2. INTRODUCTION

In December 2019 the Wuhan Municipal Health Committee identified an outbreak of viral pneumonia cases of unknown cause. Coronavirus RNA was quickly identified in some of these patients. This novel Coronavirus (nCoV) was originally referred to as 2019-nCoV but has now been named SARS-CoV-2 (due to its similarity to the Severe Acute Respiratory Syndrome [SARS] Coronavirus [CoV; SARS-CoV]). It has 89% nucleotide identity with bat SARS-like-CoVZXC21 and 82% with that of human SARS-CoV (Chan JF et al., 2020). The disease caused by SARS-CoV-2 is called Coronavirus disease 2019 (COVID-19). On January 5, 2020 there were 59 confirmed cases, 278 cases on January 20, 2118 cases on January 26, rising to more than 110,000 confirmed cases and 3996 deaths as of March 9, 2020 according to various international health reporting agencies. Outbreak forecasting and modeling suggest that these numbers will continue to rise (Wu et al., Lancet, Jan. 31, 2020). On January 30, 2020, the International Health Regulations Emergency Committee of the World Health Organization (WHO) declared the COVID-19 outbreak a Public Health Emergency of International Concern. On January 31, 2020, the US Department of Health and Human Services declared a public health emergency in the United States. On March 11, 2020 the WHO declared COVID-19 a pandemic.

Global efforts to evaluate novel antivirals and therapeutic strategies to treat SARS-CoV-2 severe infections have intensified, but no proven therapeutic currently exists. There is currently no approved vaccine against the SARS-CoV-2 virus. Therefore, there is an urgent public health need for rapid development of novel interventions. Based on currently available information and clinical experience suggesting that older adults may be at higher risk for severe illness from COVID-19, it is important to rapidly assess clinical safety of novel vaccines in this vulnerable population as early as possible. This phase 1 clinical trial proposes to evaluate safety and immunogenicity of Moderna's mRNA-1273 in healthy adults across the age spectrum (≥ 18 years of age).

ModernaTX, Inc. has developed a rapid response, proprietary messenger RNA (mRNA)-based vaccine platform. This is based on the principle and observations that antigens can be produced in vivo by delivery and uptake of the corresponding mRNA by cells. The mRNA then undergoes intracellular ribosomal translation to endogenously express the protein antigen(s) encoded by the vaccine mRNA. This mRNA-based vaccine does not enter the cellular nucleus or interact with the genome, is nonreplicating, and expression is transient. mRNA vaccines thereby offer a mechanism to stimulate endogenous production of structurally intact protein antigens in a way that mimics wild-type viral infection and are able to induce good immune responses against infectious pathogens such as cytomegalovirus (CMV) (NCT03382405), human metapneumovirus (hMPV) and parainfluenza virus type 3 (PIV3) (NCT03392389) and influenza virus (NCT03076385 and NCT03345043). ModernaTX, Inc. is using its mRNA-based technology to develop a novel LNP-encapsulated messenger RNA (mRNA)-based vaccine against SARS-CoV-2. mRNA-1273 is a novel LNP mRNA-based vaccine that encodes for the full-length spike (S) protein of SARS-CoV-2, modified to introduce two proline residues to stabilize the S protein into a pre-fusogenic form.

2.1. Purpose of the Analyses

These analyses will assess the immunogenicity and safety of mRNA-1273 vaccine at 4 different dosages (25µg, 50µg, 100 µg and 250 µg; 10 µg cohort was not enrolled) and in 3 different age cohorts: 18-55 years old, 56-70 years old, and ≥ 71 years old.

3. STUDY OBJECTIVES AND ENDPOINTS**3.1. Study Objectives and Endpoints**

OBJECTIVES	ENDPOINTS (OUTCOME MEASURES)
Primary	
To evaluate the safety and reactogenicity of a 2-dose vaccination schedule of mRNA-1273, given 28 days apart, across 5 dosages in healthy adults.	
 • Frequency and grade of each solicited local and systemic reactogenicity AE during a 7-day follow-up period post each vaccination. • Frequency and grade of any unsolicited AEs during the 28-day follow-up period post each vaccination. • Frequency of any SAEs, NOCMCs and MAAEs from Day 1 to Day 394.
Secondary	
To evaluate the immunogenicity as measured by IgG ELISA to the SARS-CoV-2 S (spike) protein following a 2-dose vaccination schedule of mRNA-1273 at Day 57.	
 • GMT of antibody at Day 57. • Percentage of subjects who seroconverted, defined as a 4-fold change in antibody titer from baseline. • The GMFR in IgG titer from baseline.
Exploratory	
To evaluate the immunogenicity as measured by IgG ELISA to the SARS-CoV-2 S (spike) protein following a 2-dose vaccination schedule of mRNA-1273 at all timepoints, other than Day 57.	
 • GMT of antibody at each timepoint. • Percentage of subjects who seroconverted at each timepoint. • The GMFR in IgG titer from baseline for each post-vaccination timepoint.
To evaluate the immunogenicity as measured by IgM and IgA ELISA to the SARS-CoV-2 S (spike) protein following a 2-dose vaccination schedule of mRNA-1273 given 28 days apart.	
 • GMT at each timepoint. • Percentage of subjects who seroconverted at each timepoint. • The GMFR in IgM and IgA titer from baseline at each post-vaccination timepoint.

OBJECTIVES	ENDPOINTS (OUTCOME MEASURES)
To evaluate the immunogenicity as measured by pseudovirus neutralization following a 2-dose vaccination schedule of mRNA-1273 given 28 days apart.	
 • GMT of Neut antibody at each timepoint. • Percentage of subjects who seroconverted, defined as a 4-fold change in Neut antibody titer from baseline at each timepoint. • The GMFR Neut antibody titer from baseline at each post-vaccination timepoint.
To evaluate the immunogenicity as measured by live wild-type SARS-CoV-2 neutralization following a 2-dose vaccination schedule of mRNA-1273 given 28 days apart.	
 • GMT of Neut antibody at each timepoint. • Percentage of subjects who seroconverted, defined as a 4-fold change in Neut antibody titer from baseline at each timepoint. • The GMFR in Neut antibody titer from baseline at each post-vaccination timepoint.
To assess, in at least a subset of samples, the SARS-CoV-2 S protein-specific T cell responses.	
 • Magnitude, phenotype, and percentage of cytokine producing S protein-specific T cells, as measured by flow cytometry at different timepoints post vaccination relative to baseline.

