## 3. OBJECTIVES AND ENDPOINTS

**Table 5: Objectives and Endpoints (Outcome Measures)**

OBJECTIVES	ENDPOINTS (OUTCOME MEASURES)
Primary	

 
To evaluate the safety and reactogenicity of a 2-dose vaccination schedule of mRNA-1273, given 28 days apart, across 5 dosages in healthy adults.
 
	
 
Frequency and grade of each solicited local and systemic reactogenicity AE during a 7-day follow-up period post each vaccination.
 
Frequency and grade of any unsolicited AEs during the 28-day follow-up period post each vaccination.
 
Frequency of any SAEs, Protocol Specified AESIs, NOCMCs, and MAAEs from Day 1 to Day 394.
 

Secondary	

 
To evaluate the immunogenicity as measured by IgG ELISA to the SARS-CoV-2 S (spike) protein following a 2-dose vaccination schedule of mRNA-1273 at Day 57.
 
	
 
GMT of antibody at Day 57.
 
Percentage of subjects who seroconverted, defined as a 4-fold change in antibody titer from baseline.
 
The GMFR in IgG titer from baseline.
 

Exploratory	

OBJECTIVES	ENDPOINTS (OUTCOME MEASURES)

 
To evaluate the immunogenicity as measured by IgG ELISA to the SARS-CoV-2 S (spike) protein following a 2-dose vaccination schedule of mRNA-1273 at all timepoints, other than Day 57.
 
	
 
GMT of antibody at each timepoint.
 
Percentage of subjects who seroconverted at each timepoint.
 
The GMFR in IgG titer from baseline at each post-vaccination timepoint.
 

 
To evaluate the immunogenicity as measured by IgM and IgA ELISA to the SARS-CoV-2 S (spike) protein following a 2-dose vaccination schedule of mRNA-1273 given 28 days apart.
 
	
 
GMT at each timepoint.
 
Percentage of subjects who seroconverted at each timepoint.
 
The GMFR in IgM and IgA titer from baseline at each post-vaccination timepoint.
 

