### **8.3.9 Adverse Events of Special Interest (AESIs)**

Adverse Events of Special Interest (AESIs) represent any events for which additional data (besides the standard AE data) are desired. These may be at the request of the regulatory agency, industry partner or DMID, and driven by a regulatory requirement, or known or potential risk from the product or class. Non-structured data similar to SAEs will be collected for AESIs. AESIs encompass the following terms:

- Protocol Specified AESIs:
  - All suspected cases of myocarditis or pericarditis should be recorded. For reporting purposes, a subject who displays signs/symptoms consistent with myocarditis or pericarditis should be reported as a potential case of myocarditis or pericarditis.
- NOCMCs – defined as any new ICD diagnosis (per current International Statistical Classification of Diseases and Related Health Problems) that is applied to the subject during the course of the study, after receipt of the study agent, that is expected to continue for at least 3 months and requires continued health care intervention.
- MAAEs – defined as hospitalization, an emergency room visit or an otherwise unscheduled visit to or from medical personnel for any reason.

All AESIs are assessed, recorded, and followed as described above under AEs. AESIs that meet SAE criteria will be reported on an SAE form within 24 hours to the DMID Pharmacovigilance Group, at the following address:

DMID Pharmacovigilance Group  
Clinical Research Operations and Management Support (CROMS)  
[name]  
[name]  
SAE Hot Line: [name] (US) or [name] (outside US)  
SAE [contact] (US) or [name] (outside US)  
SAE Email Address: [[contact]](mailto:[contact])

In addition, for documentation and medical assessment purposes AESIs that do not meet SAE criteria will also be reported on an SAE form within the period for AE reporting to the DMID Pharmacovigilance Group; however, the narrative will indicate that the AESI did not meet SAE criteria.

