9. SAFETY EVALUATION

Summaries and analysis of safety data will be presented for the Safety Analysis Population.

Solicited AEs will be summarized by severity for each day post vaccination (Days 1-8) and as the maximum severity over all 8 days. Additionally, solicited AEs will be analyzed by taking the most severe response over the follow-up period, dichotomizing into a binary variable (none versus mild, moderate, or severe) and using standard techniques, such as exact confidence intervals (CI), to summarize the proportion of subjects reporting each symptom, any application site symptom, and any systemic symptom.

Unsolicited non-serious AEs will be collected from the time of first vaccination through 28 days after the last vaccination. Unsolicited AEs will be coded by MedDRA[®] for preferred term and system organ class (SOC). All SAEs, MAAEs and NOCMCs will be collected from the time of first vaccination through the end of the study (Day 394). The numbers of SAEs and MAAEs will be reported by detailed listings showing the event description, MedDRA[®] preferred term and SOC, relevant dates (vaccinations and AEs), severity, relatedness, and outcome for each event. Non-serious unsolicited AEs will be summarized as number and percentage of subjects reporting at least one event in each MedDRA[®] preferred term and SOC, cross-tabulated by severity and relationship to study product. Additionally, the proportion of subjects and exact 95% CIs of AEs in aggregate and by MedDRA[®] categories will be computed.

Clinical laboratory data will be summarized by severity and relationship for each visit, and as the maximum over all post-vaccination visits. Graphical presentations will include bar plots.

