9.3.2. Unsolicited Adverse Events

The proportion of subjects reporting at least one unsolicited adverse event will be summarized by MedDRA system organ class and preferred term for each vaccination and over all vaccinations.

Denominators for percentages are the number of subjects who received the vaccination being summarized.

Adverse events by subject will be presented in [Listing 12](#).

The following summaries for unsolicited adverse events will be presented by MedDRA system organ class, preferred term, vaccination and Treatment Group:

- Subject incidence and total frequency of adverse events (starting at [Table 216](#) and ending at [Table 228](#));
- Summary of severity and relationship to study product (starting at [Table 229](#) and ending at [Table 241](#));
- Subject incidence and total frequency of adverse events over time (starting at [Table 242](#) and ending at [Table 254](#));
- Subject listing of non-serious adverse events of moderate or greater severity ([Table 256](#));
- Listing of MAAEs and NOCMCs ([Table 257](#));
- Bar chart of non-serious adverse events by severity and MedDRA system organ class ([Figure 176](#), [Figure 177](#), and [Figure 178](#));
- Bar chart of non-serious adverse events by severity ([Figure 179](#), [Figure 180](#), and [Figure 181](#)).

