9.4. Deaths, Serious Adverse Events and other Significant Adverse Events

The following listings will be presented including Subject ID, Age (years) Adverse Event Description, Adverse Event Onset Date/End Date, Last Dose Received/Days Post Dose, Reason Reported as an SAE, Relationship to Treatment, Alternate Etiology if not Related, Outcome, and Duration of Event (days):

- Deaths and Serious Adverse Events ([Table 255](#));
- New Onset Chronic Medical Conditions and Medically Attended Adverse Events ([Table 257](#)).

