9.5.1 Efficacy/Immunogenicity and Safety Measurements Assessed and Flow Chart

Table 2: Schedule of Study Procedures*

Procedures	Screening Visit 00, Day -42 to -1	Enrollment/Baseline Visit 01, Day 1	Visit 02, Day 2 1 day post Dose 1	Visit 03, Day 3 2 days post Dose 1	Visit 04 Day 8 +/- 1 day	Visit 05 Day 15 +/- 2 days	Visit 06 Day 29 +/- 2 days	Visit 07, Day 30 1 day post Dose 2	Visit 08, Day 31 2 days post Dose 2	Visit 09 ^f Day 36 +/- 1 day	Visit 10 ^f Day 43 +/- 2 days	Visit 11 ^f Day 57 +/- 2 days	Visit 11A ^f Day 71 -7/+ 21 days	Visit 12 ^f Day 119 +/- 7 days	Visit 13 ^f Day 209 +/- 7 days	Final Study Visit 14 ^f Day 394 +/- 14 days	Unscheduled Visit	Early Termination Visit
Informed Consent	X																	
Review Eligibility Criteria	X	X					X											
Medical History	X																	
Concomitant Medications	X	X	X	X	X	X	X	X	X	X	X	X		X	X	X	X	X
Vaccination		X					X											
Telephone Contact			X	X				X	X									
Interim History		X			X	X	X			X	X	X		X	X	X	X	X
Physical Examination ^a	X	X			X	X	X			X	X	X		X	X	X	X	X
Vital Signs	X	X			X	X	X			X	X	X		X	X	X	X	X
Height and Weight (for BMI)	X																	
Hematology ^b	X	X			X		X			X								
Chemistry ^b	X	X			X		X			X								
Serology ^b	X																	
Pregnancy Test ^c	X	X					X											
Urine Drug Screen	X																	
Memory Aid: Solicited AEs			Days 1-8				Days 29-36											
Unsolicited AEs			Days 1-57															
SAEs, MAAEs and NOCMCs			Days 1-394															
Serum for Serological Immunogenicity Assays		X				X	X			X	X	X		X	X	X		X
Peripheral Blood Mononuclear Cells (PBMCs) for Cellular Immunology Assays		X				X	X			X	X	X		X	X			X
Serum for Secondary Research ^d		X				X	X			X	X	X		X	X	X		X
Serum for Product Assay Development		X				X	X			X	X	X		X	X	X		X
Leukocytes for Secondary Research (subset of subjects)													X ^e					

- a) Full physical examination will be performed at screening and symptom-directed (targeted) physical examination at all other timepoints if indicated.
- b) Clinical screening laboratory evaluations will include WBCs, Hgb, PLTs, Cr, ALT, AST, ALP, T. Bili, Lipase, PT, PTT, hepatitis B surface antigen, hepatitis C virus antibody, and HIV types 1 and 2 antigen/antibody. Clinical safety laboratory evaluations obtained on Days 1, 8, 29, and 36 will include WBCs, Hgb, PLTs, Cr, ALT, AST, ALP, T. Bili, and Lipase.

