14.3 Safety Data

14.3.1 Displays of Adverse Events

Table 138: Overall Summary of Adverse Events by Treatment Group - All Subjects 18-55 Years of Age*

Subjects ^a with		25 µg mRNA-1273 (N=X)		50 µg mRNA -1273 (N=X)		100 µg mRNA -1273 (N=X)		250 µg mRNA -1273 (N=X)		All Subjects (N=X)	
Category 1	Category 2	n	%	n	%	n	%	n	%	n	%
At least one local solicited adverse event	NA										
At least one systemic solicited adverse event	NA										
At least one unsolicited adverse event	NA										
At least one related unsolicited adverse event	Any Grade										
	Mild (Grade 1)										
	Moderate (Grade 2)										
	Severe (Grade 3)										
At least one severe (Grade 3) unsolicited adverse event	Any relationship										
Related	Related										
Unrelated	Unrelated										
At least one serious adverse event ^b	Any relationship										
	Related										

Subjects ^a with		25 µg mRNA-1273 (N=X)		50 µg mRNA -1273 (N=X)		100 µg mRNA -1273 (N=X)		250 µg mRNA -1273 (N=X)		All Subjects (N=X)	
Category 1	Category 2	n	%	n	%	n	%	n	%	n	%
At least one adverse event leading to early termination ^c	NA										
Any laboratory Adverse Event											
Any Vitals Signs Adverse Event											
At least one medically attended adverse event	NA										
At least one new onset chronic medical condition	NA										

N = Number of subjects in the Safety Population
^aSubjects are counted once for each category regardless of the number of events.
^bA listing of Serious Adverse Events is included in [Table 255](#).
^cAs reported on the Adverse Event eCRF.

Tables with Similar Format:

Table 139: Overall Summary of Adverse Events by Treatment Group - All Subjects 56-70 Years of Age*

Table 140: Overall Summary of Adverse Events by Treatment Group - All Subjects ≥71 Years of Age*

Table 141: Serious Adverse Events and Non-Serious Adverse Events Occurring in 5% of Subjects in Any Treatment Group by MedDRA System Organ Class and Preferred Term, and Treatment Group - All Subjects 18-55 Years of Age

Preferred Term	MedDRA System Organ Class	25 µg mRNA-1273 (N=X)			50 µg mRNA -1273 (N=X)			100 µg mRNA -1273 (N=X)			250 µg mRNA -1273 (N=X)			All Subjects (N=X)		
		n	%	Events	n	%	Events	n	%	Events	n	%	Events	n	%	Events
Serious Adverse Events																
All	All	x	x	x	x	x	x							x	x	x
PT1	SOC1	x	x	x	x	x	x							x	x	x
Etc.	Etc.															
Other (Non-serious) Adverse Events																
All	All	x	x	x	x	x	x							x	x	x
PT1	SOC1	x	x	x	x	x	x							x	x	x

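### The SAP's third primary endpoint omits Protocol Specified AESIs (suspected myocarditis or pericarditis), and no SAP display counts them as a class

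*SAP*

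**What the plan says.** **Protocol.** The third primary endpoint, in the synopsis (Table 2) and in Section 3 (Table 5), is "Frequency of any SAEs, Protocol Specified AESIs, NOCMCs, and MAAEs from Day 1 to Day 394". Section 8.3.9 defines the protocol-specified class: "All suspected cases of myocarditis or pericarditis should be recorded". It adds that a subject with consistent signs or symptoms is to be reported as a potential case. Under Section 8.3.1 these events continue to be reported as AEs after Day 57, through Day 394.

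**SAP.** Section 3.1 states the same endpoint as "Frequency of any SAEs, NOCMCs and MAAEs from Day 1 to Day 394". The same three classes recur wherever the SAP deals with long-term events:

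- the design text (4.1) and the opening of Section 9, which collect SAEs, MAAEs and NOCMCs through Day 394;
- Section 9.3.2, which plans a "Listing of MAAEs and NOCMCs" (Table 257);
- Section 9.4, which besides deaths and SAEs names only "New Onset Chronic Medical Conditions and Medically Attended Adverse Events";
- the schedule (Table 2), whose row reads "SAEs, MAAEs and NOCMCs";
- the overall AE summary (Tables 138-140), with separate rows for SAEs, MAAEs and, for example, "At least one new onset chronic medical condition".

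The supplied SAP never uses the term AESI. It mentions myocarditis and pericarditis only in an exclusion criterion.

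**The concern.** Protocol 8.3.9 groups three kinds of event under AESIs: the protocol-specified class, NOCMCs and MAAEs. The SAP gives the last two a row each in Tables 138-140 and a column each in Table 257. The protocol-specified class, added for a named vaccine risk, has neither.

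The endpoint is the frequency of a class of event. If the final analysis follows the SAP as written, that frequency is not produced for one of the classes, and the primary safety objective is only partly answered. A reader wanting to know how many suspected cases occurred, in which cohort and after which dose, would have to reconstruct the answer from tables organised by system organ class (SOC) and preferred term.

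**Working it through.** No planned figure is at issue, so the check is mainly a comparison of texts.

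**Step 1. Count the components.**

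| Event class | Protocol, third primary endpoint | SAP 3.1 | Row in Tables 138-140 | Dedicated listing |
|---|---|---|---|---|
| SAE | yes | yes | yes | Table 255 |
| MAAE | yes | yes | yes | Table 257 |
| NOCMC | yes | yes | yes | Table 257 |
| Protocol Specified AESI | yes | no | no | none |

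Four classes in the protocol, three in the SAP. There is no dedicated AESI row, column, table or listing.

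**Step 2. Trace a suspected case through the SAP.** Section 9.3 puts every reported AE into the summaries. A non-serious case would therefore enter:

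- the unsolicited-AE row of Tables 138-140;
- Tables 216-228 by SOC, which include a Cardiac Disorders row;
- Tables 229-254 by SOC and preferred term;
- Table 256 if moderate or severe;
- Listing 12.

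If serious it would also be in Table 255. If medically attended or a NOCMC it would also be in Table 257 and the matching row of Tables 138-140. None of these displays marks it as an AESI.

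**Step 3. Ask whether the class can be counted from those displays.** Protocol 8.3.9 sets the threshold at consistent signs or symptoms. Protocol 2.2.1 names chest pain, shortness of breath, tachycardia and palpitations. A case recorded as a symptom need not be coded to Cardiac Disorders: the SAP's own mock-up of Table 229 puts exertional dyspnoea under the respiratory class. In the other direction, a Cardiac Disorders count can include events that are not suspected myocarditis or pericarditis. Protocol 8.3.6.1 asks sites to group related signs and symptoms under one diagnosis, so scattering is possible rather than certain. Either way, the count needs an AESI flag that no display carries.

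**Step 4. Find the weakest coverage.** A case that is non-serious, not medically attended and not chronic is outside Tables 255 and 257 and outside the SAE, MAAE and NOCMC rows. If mild, it is also outside Table 256. It then rests on the generic tables and Listing 12 alone.

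**Step 5. Size of one case.** The enrolled cohorts have 15 subjects (four cohorts) or 10 (six cohorts). For one event in n, the exact (Clopper-Pearson) limits are:

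- lower = 1 − 0.975^(1/n);
- upper = the p that solves (1 − p)^n + n·p·(1 − p)^(n−1) = 0.025.

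| n | 1/n | Lower | Upper |
|---|---|---|---|
| 15 | 6.7% | 0.2% | 32% |
| 10 | 10% | 0.3% | 45% |

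These are illustrations of what an AESI row would show for a hypothetical single case. They do not measure information lost.

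**The case against.** **The event would not be lost.** A reader might infer that a suspected case appears in no summary, or only as an unflagged line in Listing 12. The documents do not support that: Step 2 shows several generic displays that would carry it. The MAAE definition is also broad, covering any unscheduled medical visit for any reason, and protocol 2.2.1 encourages subjects with such symptoms to contact research staff and their medical providers at once. Many cases would therefore reach Tables 138-140 and 257 as MAAEs. Non-serious AESIs also go to pharmacovigilance on an SAE form, and the SAP reserves a place in the study report for narratives of significant events. All of this stands. It limits the point to the missing count of the class.

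**The SAP may simply predate the change.** AESIs entered with protocol version 7.0 (July 30, 2021). The SAP has no third-dose substudy, describes an interim report as still to come and says no vaccine is approved, so it seems to match an earlier protocol. Its date is not visible. A reader might infer a decision to leave the event out; nothing in the documents supports that. Version lag is the likelier explanation, but it does not close the gap. The SAP's preface claims to cover all planned analyses and to include the displays for the final ones, and its Section 15 records no changes.

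**The protocol names no AESI display either.** This is correct: protocol 9.4.4 collects AESIs but prescribes listings only for SAEs and MAAEs. That leaves the SAP as the place to specify one. It also means the exact layout is a choice.

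**Little prospective capture may have remained.** The enrollment start date is not given. Assume it fell between version 2.0 (March 13, 2020) and version 3.0 (March 30, 2020). Adding the stated 16 weeks of enrollment (112 days) and 393 days to Day 394 puts the last subject's final visit between July 31 and August 17, 2021, before the ±14-day window. On that assumption most main-study follow-up preceded version 7.0. This stands, and it is why the fix needs a rule for earlier cases.

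**Conclusion.** The SAP is wrong as written on this point. It contradicts the current protocol by dropping one of the four event classes in the third primary endpoint, and no table or listing identifies or counts that class. The consequence is a primary-endpoint frequency that is not reported; individual cases would still be visible in generic displays. The trial has no hypothesis test, so no error rate or power is affected. The change should be made, and it is cheap.

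The conclusion rests on two assumptions: that the supplied SAP is the one governing the final analysis, and that the version 7.0 endpoint applies to the main study, as its Table 5 states. If a later SAP already carries the class, the point falls away.

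**What to change.** 1. Add Protocol Specified AESIs to SAP 3.1, 4.1, 9, 9.3.2, 9.4 and Table 2, matching the protocol's endpoint.
2. Add an AESI row (n, %) to Tables 138-140, with the exact 95% CI that Section 9 already plans for AE proportions.
3. Add an AESI column to Table 257.
4. State that non-serious suspected cases count, whether or not they are medically attended or chronic.
5. State how cases recorded before protocol version 7.0 are identified from the AE data, for example by a prespecified list of preferred terms, including symptom terms, followed by medical review.

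Items 1 to 4 cost SAP wording, one row and one column; the protocol already requires the data from version 7.0 on. Item 5 costs a retrospective review of AEs already recorded, for 120 enrolled subjects. The report should say that cases found this way were not captured prospectively.
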